12.6. Appendix 6 - 24 hour Dietary Recall

Screening Number _____ Visit Number _____

Date: ___/___/___ (DD/MMM/YYYY)

Is this a typical day? Yes or No _____

To parents/LARs

"I am going to ask you about everything that (NAME OF CHILD) ate and drank yesterday. By this I mean, 24 hours from midnight to midnight. I would like to know exactly what was eaten and drank and how much (NAME OF CHILD) had."

To Child

"I will ask you to tell me about any foods and drinks which your (MUM, DAD (main food provider)) does not know about or cannot remember. Is that okay? [Wait for agreement]."

	Food/beverage Item	Description (Homemade/Bought)	Portion Size	Recipe ¹ (¹Applicable only if homemade)	Brand ² (²Applicable only if bought)
Morning					
Morning Snacks					

Document Name	Clinical Study Protocol 204477		
Type	Version	Document Identifier	Effective Date
eldo_clinical_doc	5.0; Most-Recent; Effective; CURRENT	090032d580daa95e	10-Oct-2017 06:16:49
Reason For Issue	Auto Issue		

	Food/beverage Item	Description (Homemade/Bought)	Portion Size	Recipe¹ (¹Applicable only if homemade)	Brand² (²Applicable only if bought)
Lunch					
Evening Snacks					
Dinner					

Document Name	Clinical Study Protocol 204477		
Type	Version	Document Identifier	Effective Date
eldo_clinical_doc	5.0; Most-Recent; Effective; CURRENT	090032d580daa95e	10-Oct-2017 06:16:49
Reason For Issue	Auto Issue		

	Food/beverage Item	Description (Homemade/Bought)	Portion Size	Recipe¹ (¹Applicable only if homemade)	Brand² (²Applicable only if bought)
Any other Food/Beverage					

Completed by-
Name:

Signature & Date:

 GlaxoSmithKline	Document Name	Clinical Study Protocol 204477		
	Type	Version	Document Identifier	Effective Date
	eldo_clinical_doc	5.0; Most-Recent; Effective; CURRENT	090032d580daa95e	10-Oct-2017 06:16:49
	Reason For Issue	Auto Issue		

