	Type	Version	Document Identifier	Effective Date
	eldo_clinical_doc	5.0; Most-Recent; Effective; CURRENT	090032d580daa95e	10-Oct-2017 06:16:49
	Reason For Issue	Auto Issue		

Amendment No. & New Protocol Version No.	Type of Amendment	Reason for Amendment	Other Documents Requiring Amendment	Section(s) Amended	PI Amendment Agreement Signature & Date
		SOP, timeline of writing statistical reporting and analysis plan is changed from 'prior to study start (first subject first visit (FSFV))' to 'study analysis'.	CRF  Yes  No		

	Document Name	Clinical Study Protocol 204477		
	Type	Version	Document Identifier	Effective Date
	eldo_clinical_doc	5.0; Most-Recent; Effective; CURRENT	090032d580daa95e	10-Oct-2017 06:16:49
	Reason For Issue	Auto Issue		

SCHEDULE OF EVENTS

Activity	Visit 1	Visit 2	Dietary Counselling Visits ¹		SPWR & parent/LAR symptom checklist	Visit 10					
	Screening Visit	Baseline Visit (+1 to 21 days post screening visit)	Visit 3: Session 1-Day1-3 of Week 1 from BV	Visit 4: Session 2-Week 2 from BV+ up to 3 days		Visit 5: Session 3-Week 6 from BV+ up to 3 days	Visit 6: Session 4-Week 10 from BV+ up to 3 days	Visit 7: Session 5-Week 14 from BV+ up to 3 days	Visit 8: Session 6-Week 18 from BV + up to 3 days	Visit 9: Session 7-Week 22 from BV + up to 3 days	End of Study Visit (+ 1 to 7 days post end of 9 month from baseline visit)
Informed consent and assent ²	X										
Demographics	X										
Medical history	X										
Current/concomitant medication	X	X			X						X
General physical examination	X										X
Vital signs	X										X
Hb assessment using Pronto	X										
Anthropometric measurements (height, weight, BMI and HAZ)	X										X
Inclusion/exclusion criteria evaluation	X										
Subject Eligibility	X										
24 hr dietary recall & Dietary Diversity Survey	X										X
Parental/LAR training to complete 'symptom check list' ³	X										
Dispense blank Parent/LAR symptom checklist and Product Compliance Report Forms	X										
Continued eligibility criteria		X			X						X
Sample collection for urinary neopterin test & lactulose/mannitol test		X									X
Sample collection for analysis of serum ferritin, sTfR, CRP, AGP, sIgA & nutritional biochemistry		X									X
Dietary counselling											X
Product administration (applicable to test group only) ⁴											X
Product compliance check & collect empty product sachet (applicable to test group only)											X

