AE monitoring		X			X						X
Study Completion and medical sign off											X

¹ Session number 3, 4, 5, 6 and 7 can be postponed in view of long school holidays and exams. Session no 7 will not be conducted any later than the last day of 8th month of intervention period. A minimum of 4 weeks gap must be maintained between session number 2, 3, 4, 5, 6 and 7.

² Obtaining informed consent and assent and performing screening activities can be on different dates but informed consent and assent will be obtained prior to performing and applying any screening criteria or procedures. Screening activities should be within 60 days of obtaining consent and assent.

³ Can be done anytime post obtaining Consent & Assent but prior to baseline visit.

⁴ Intervention begins +1 to 3 days from baseline visit and continues for 9 months. Compliance check, test product empty sachets will be collected and AE will be recorded throughout the intervention period.

 GlaxoSmithKline	Document Name	Clinical Study Protocol 204477		
	Type	Version	Document Identifier	Effective Date
	eldo_clinical_doc	5.0; Most-Recent; Effective; CURRENT	090032d580daa95e	10-Oct-2017 06:16:49
	Reason For Issue	Auto Issue		

PROTOCOL SYNOPSIS FOR STUDY 204477

Brief Summary

The importance of public health intervention lies with the concept of the ‘Continuum of care’ approach. While there already exists a lot of information on the prevalence of nutritional inadequacy and its effects on morbidity and mortality from common childhood illnesses for children under 5 years of age, unfortunately, similar information on children older than 5 years of age is scarce. A nutritional intervention program will benefit an adolescent age group (11-19 years) only if there is continuity of care for primary school age children (6-10 years) also.

There is a wide-spread prevalence of concurrent micronutrient deficiencies, even in apparently normal school age children in India. Sometimes even apparently healthy school children may have sub-clinical deficiencies. Various studies and dietary surveys such as those conducted by the Indian Council of Medical Research indicate that the micronutrient intakes of school age children in India are much below the recommended levels.

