Background diets and changes in background diets may distort the true relationship between the intervention and the outcome. To eliminate such possible confounding, it is imperative that quality of dietary intakes is assessed both at start and end of study. Since, quality of a diet is impacted by food quantity and diversity; both these variables will be assessed for all study participants. For quantitative assessment of food consumption, 24-hour dietary recall will be used. To understand the diversity of foods that the child is consuming, a 24-hour Individual Dietary Diversity Score (IDDS) [FAO guidelines dietary diversity, 2011] will be used.

Cluster sampling design may impact effective sample size, which can be mitigated using more numbers of clusters. Thus, considering feasibility, at least 2 schools per study group will be selected.

To control for possible effects of gender, a balanced ratio of boys and girls in the test and control groups will be targeted. The study will be stratified by gender to recruit a target ratio of 50% girls and 50% boys, with a minimum of 40% of either gender and a maximum of 60% of either gender.

 GlaxoSmithKline	Document Name	Clinical Study Protocol 204477		
	Type	Version	Document Identifier	Effective Date
	eldo_clinical_doc	5.0; Most-Recent; Effective; CURRENT	090032d580daa95e	10-Oct-2017 06:16:49
	Reason For Issue	Auto Issue		

The study flowchart will be as follows:

 GlaxoSmithKline	Document Name	Clinical Study Protocol 204477		
	Type	Version	Document Identifier	Effective Date
	eldo_clinical_doc	5.0; Most-Recent; Effective; CURRENT	090032d580daa95e	10-Oct-2017 06:16:49
	Reason For Issue	Auto Issue		

Rationale for Participants' Inclusion and Exclusion:

With the assumption that the study population is normally distributed for World Health Organisation (WHO) height-for-age z-scores (HAZ), reference populations within -2 to +2 standard deviations (or z score) represent 95.4 % population. But for the study participants in developing countries like India, the median for the HAZ in comparison to WHO growth standards is towards the lower side which falls at approximately -2 SD of the WHO standard curve at age 5 years [National Family Health Survey -3] [Indian Academy of Paediatrics Growth Charts Committee, 2015]. Thus a Z-score between -3 to -1 (rather than -2 to +2) would cover the representative population of developing countries like India.

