Availability of physician will also ensure the children are provided with timely care, which could include the advice to use a hydration formula and/or medications (*e.g.*, antibiotic, nasal decongestant) to help manage their symptoms/infection. If and when needed, and, if possible, the same type of hydration formulas and medications would be provided to children – *e.g.*, the same type of antibiotic, the same type of nasal decongestant, *etc.*

6.13. 24 hr Dietary Recall & Dietary Diversity Survey

6.13.1. 24 hr Dietary Recall

This method involves a structured interview and will be conducted as per the questionnaire provided in Appendix 6. Since children, invariably tend to overestimate, parents/LARs should be present at the 24-hour recalls. Majority of the information should come from the parent/LARs, with the child making additions to fill in the gaps.

Respondents (participant/ Parents/LARs) will also be asked whether or not the day recalled is typical of their usual food consumption, or if it was unusual or restricted in any way *e.g.* fast, festival *etc.* If the day is not the representative of a typical day then the participant may be called for another day.

On confirmation of the day being a representative of a typical day, a trained study staff will ask the respondents (participant/ parents/LARs) to recall all food and beverage consumed by the child during previous 24 hours. For homemade food and beverage, following information will be recorded:

- List of ingredients: *e.g.* water, oil, herbs, spices.
- Amounts of ingredients: This can be in household measures, weights or using portion sizes.
- Cooking method: Record some brief information on how the dish was prepared and cooked.

 GlaxoSmithKline	Document Name	Clinical Study Protocol 204477		
	Type	Version	Document Identifier	Effective Date
	eldo_clinical_doc	5.0; Most-Recent; Effective; CURRENT	090032d580daa95e	10-Oct-2017 06:16:49
	Reason For Issue	Auto Issue		

The food or beverage items which are bought, name of the brand will be enquired. A portion size can be described in terms of either household measures (e.g. one level teaspoon of sugar, bowl, cup etc) or weights.

Calculation on energy and the macronutrients (protein, carbohydrates and fat) will be made using application/software. For the purpose latest available Dietsoft software available at <http://dietsoft.in/> based on Indian data (NIN and ICMR) will be used.

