4.3.1 Study Product Compliance and Exposure

For doses administered at school, study-personnel will supervise and ensure complete consumption of test product.

The descriptive summary of total number of expected amount of product to be consumed, actual amount product consumed by product group and overall for all participants in mITT population (Table 14.2.1.1).

The compliance will be calculated using following formula –

Test product compliance:

Test product compliance = Actual Consumption X 100/Expected Consumption

Where, actual and expected consumption are defined below:

- Expected consumption = (2X 150 mL of drink X number of days* between first and last treatment day in the study)
- Actual consumption = Expected consumption – (xx mL total left over at morning + xx mL left over at evening)]

*up to maximum of 9 months (to be converted in days) (as test product is only administered maximum up to 9 month regardless last visit day in study)

Dietary Counselling Compliance:

The dietary counselling compliance will be calculated using following formulas:

- **Participants:**
 - Compliance with Mandatory dietary counselling= (Number of sessions out of session numbers 1 or 2 attended by participant divided by 2) X 100
 - Compliance with Follow-up sessions dietary counselling= (Number of sessions out of session numbers 3-7 attended by participant divided by 5) X 100
- **Parents/LAR:**
 - Compliance with Mandatory dietary counselling= (Number of sessions out of session numbers 1 or 2 attended by parents/LAR divided by 2) X 100
 - Compliance with Follow-up sessions dietary counselling= (Number of sessions out of session numbers 3-7 attended by parents/LAR divided by 5) X 100

Study product compliance listing ([Listing 16.2.5.1](#)) using enrolled population will be presented at the time of blinded data review process. Noncompliance will be assessed on a participant by participant basis. Those participants with product compliance less than 70% or non-compliant with dietary counselling will be excluded from the PP population. Any participant excluded from PP population will be clearly documented in the population definition document.

Exposure to the study product in days will be calculated as date of last day in the study minus date of first date of study product administration +1 for the test group.

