| 
 9.3.5 | 
The following analysis was removed
 
 Total number of ill days (GI and respiratory illnesses), number of episodes (GI and respiratory illnesses), and severity of GI and respiratory illnesses by screening, end of study, and change from baseline in DDS, energy, protein, carbohydrate and fat. | 
 It will be part of potential post-hoc analysis decided after study un-blinding if imbalances between product groups are observed for the variables. |

| Protocol | Reporting & Analysis Plan | |
|--|---|--|
| Statistical Analysis section | Statistical Analysis Plan | Rationale for Changes |
| 
 9.3.2 9.3.3 9.3.5 | 
 Baseline IDDS has been added in the statistical model as covariate for the primary, secondary and other analysis since baseline IDDS has an impact on these analyses. | 
 Morbidities are the important endpoints (both primary and secondary) in this study and scientific evidences suggest that these outcomes are associated with dietary diversity score (Oduor et al., 2013) (Kiboi et al., 2016). Also, factors such as nutritional and socioeconomic status which play important role in immunity status of children are also associated with dietary diversity. Dietary diversity is associated with socio-economic status and household food security (Hoddinot & Yohannes, 2002; Hatloy et al., 2000). IDDS has been validated for several age/sex groups as proxy measures for macro and/ or micronutrient adequacy of the diet (FAO guidelines dietary diversity, 2011). Thus, the background diet is a major possible confounder in this nutritional intervention study. It thus becomes pertinent that confounding due to dietary intake measured through IDDS is controlled during statistical analysis. |
| 
 RAP Amendment 1 | | |
| 
This RAP Amendment 1 provides details of modified analyses requested from the analysis described in the Statistical Reporting and Analysis Plan (final version 1.0). The section below provides a summary of the analysis with the justification for the request.
 | | |
| Protocol | Reporting & Analysis Plan | |
| Statistical Analysis section | Statistical Analysis Plan | Rationale for Changes |

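### The end-of-study diet recall mixes product and product-free days in the test arm, with no rule for counting the study drink, so the energy and macronutrient contrast (objective 11) cannot be read as a change in background diet

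*Protocol*

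**What the plan says.** **Purpose.** Protocol 3.4 gives the reason for measuring diet: "Background diets and changes in background diets may distort the true relationship between the intervention and the outcome". Quantity is assessed by 24-hour recall and diversity by the IDDS, at the start and end of the study.

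**Timing.** The Schedule of Events places the recall at screening and at one later point, the "End of Study Visit (+ 1 to 7 days post end of 9 month from baseline visit"). Its footnote 4 says "Intervention begins +1 to 3 days from baseline visit and continues for 9 months". SAP 4.3.1 caps the dosing period, "as test product is only administered maximum up to 9 month regardless last visit day in study".

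**Content.** Protocol 6.13.1 asks respondents "to recall all food and beverage consumed by the child during previous 24 hours". Appendix 6 defines the period as the previous day, midnight to midnight: "I am going to ask you about everything that (NAME OF CHILD) ate and drank yesterday". The IDDS is filled in from the same recall (6.13.2, Appendix 7). There is an optional check for typicality: "If the day is not the representative of a typical day then the participant may be called for another day". It does not mention product status.

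**Analysis.** SAP 4.4.2 models change from baseline in IDDS, energy, protein, carbohydrate and fat with school, product group, gender and the baseline value. No term or rule concerns the study drink or whether the recalled day was a dosing day.

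**The concern.** The recall has to show whether what children eat apart from the product changed differently in the two arms. In the control arm every recall does that. In the test arm a recall may include two servings of the drink or none, depending on the start date, the visit date and whether the respondent or interviewer enters the drink at all. School-day doses are given at school (5.3), while 6.13.1 expects most of the information from the parent, so entry could differ between children. The homemade/recipe and bought/brand columns of Appendix 6 do not obviously fit a study sachet.

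A difference in energy or macronutrients could therefore come from the supplement, from a change in ordinary eating, or from a blend of the two. The reader of the report could not tell which from the planned tables.

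**Working it through.** **Plan's own figure.** The documents give no sample size for the diet objectives; Protocol 9.1 says secondary objectives were not considered in sizing. The only count used here is the planned number of completers per arm: 215 × 1.5 = 322.5, rounded up to 323, which agrees with 9.1.

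**Inputs.** Start lag s = 1, 2 or 3 days after baseline, duration nine months (Schedule of Events, footnote 4). Visit offset e = 1 to 7 days after the nine-month mark (Schedule of Events). Recalled day = the day before the visit (Appendix 6). Daily amount = 2 × 27 g = 54 g (Protocol 5.1).

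**Which day is recalled.** Call the nine-month mark from baseline day 0. The recalled day is e − 1. The last dose falls on day s − 1 if nine months is counted inclusively of the first day, or day s if not. The recalled day is a product day when it is no later than the last dose.

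- Inclusive count: e − 1 ≤ s − 1, so e ≤ s. Qualifying visit days for s = 1, 2, 3 are 1, 2, 3, giving 6 of 21 combinations = 28.6%.
- Non-inclusive count: e − 1 ≤ s, so e ≤ s + 1. Qualifying visit days are 2, 3, 4, giving 9 of 21 = 42.9%.

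With start and visit days uniform over their windows, and doses taken as scheduled, 29% to 43% of test-arm recalls are product days and 57% to 71% are not. Applied to 323 completers, that is about 92 (323 × 6/21) to 138 (323 × 9/21) product-day recalls. By start lag, the share runs from 1/7 to 3/7 (14% to 43%) under the inclusive count and from 2/7 to 4/7 (29% to 57%) under the other. If all visits fell late in the window it would be zero.

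**Possible size in energy.** The product's energy content is not shown, so I assume 3.5 to 4.2 kcal/g. I also assume that the drink is entered in full when taken and that ordinary eating is unchanged. A product day then adds 54 × 3.5 = 189 to 54 × 4.2 = 227 kcal.

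| Share on product | At 3.5 kcal/g | At 4.2 kcal/g |
|---|---|---|
| 6/21 | 54 kcal | 65 kcal |
| 9/21 | 81 kcal | 97 kcal |

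The test-arm mean would shift by about 54 to 97 kcal/day. The bounds are 0 (no recalls on product) and 189 to 227 (all on product). The control arm has no such shift.

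**Consistency of the windows.** Take s = 3 and e = 1. The visit is on day 1; nine months of product end on day 2 or day 3. The end visit can therefore precede completion of the product period under either way of counting.

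**The case against.** **The drink may not be counted.** A reader might infer from the all-inclusive wording that it is entered as diet. The documents do not say so; they are silent. This stands as a correction of emphasis, but silence leaves the entry to each interviewer, which is the problem.

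**The information is recoverable.** It is tempting to conclude that the diet objectives cannot show anything about background diet. That is too strong. Appendix 6 is dated and itemised, daily consumption goes into the CRF (5.5), and SAP Listing 16.2.1.1 carries the last administration date. An analyst could classify the days, and subtract the drink where it was entered recognisably. Control recalls and off-product test recalls give product-free intake directly. All this stands; what is missing is any instruction to do it.

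**Objective 11 is worded as consumption, so counting the drink is legitimate.** Fair on the literal text. But as total intake during supplementation the measure misses the product on the off-product recalls, and as background diet it may include the product on the others. Neither reading is clean.

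**Displacement is missed.** One might argue that any displacement of food by the drink vanishes once dosing stops. No passage says how quickly diet reverts, so this is only a possibility. The caution that the first days off product may not represent diet on product remains.

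**IDDS.** It counts each of nine food groups once. A malt-based drink would plausibly score as a starchy staple, probably already earned from ordinary meals. A milk point would depend on the product profile, which is not shown. Objective 10 is therefore much less exposed.

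**Link to the illness results.** The primary model uses baseline IDDS (SAP 4.4.1.2), taken at product-free screening (SAP 3.1). A reader might take SAP section 5 to make diet imbalances a trigger for further analyses of ill days. It removes the illness-by-diet analysis and says only: "It will be part of potential post-hoc analysis decided after study un-blinding if imbalances between product groups are observed for the variables". That is a contingency, not a decision rule.

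**Conclusion.** The point holds for energy and macronutrients. The plan's own windows and recall wording permit a mix of product and product-free days in the test arm only, and nothing in the protocol or SAP separates the drink from the rest of the diet. As planned, the objective 11 contrast cannot serve the purpose given in Protocol 3.4.

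The 29% to 43% share rests on uniform start and visit days and on dosing as scheduled. The 54 to 97 kcal shift rests in addition on an assumed energy density and on full entry of the drink. No variability for energy intake is given, so I do not claim that a shift of this size is large relative to the precision of the comparison. The primary analysis is untouched. This is a secondary-endpoint weakness worth fixing because the remedy costs so little.

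The overlap of the start and end-visit windows is a separate inconsistency.

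**What to change.** 1. In Protocol 6.13.1 and Appendix 6, record the study product as its own flagged item and record whether the recalled day was a product day.
2. In SAP 4.4.2, define energy, macronutrients and IDDS computed without the product as the background-diet measures for analysis. Show totals with the product separately, and summarise test-arm recalls by product-day status.
3. Reconcile the end-visit window in the Schedule of Events with footnote 4, since together they allow an end visit before nine months of product are complete.

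The cost is one extra form line, the day-status entry and one extra set of tables. If recalls have already been taken, visit and dosing dates still allow days to be classified, but the product can be removed only where it was entered recognisably.

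Moving the interview to a late weekly review is not needed. The weekly review is a physician's collection of symptom checklists (6.12.1), whereas the recall needs the parent and trained staff, so the move is a debatable trade-off.
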